**Visit 18 (Week 94):** The subject will have a routine clinical evaluation and a BVAS assessment. We will collect information on adverse events, concomitant medications, and medication compliance. The subject will be asked to complete a quality of life questionnaire. We will collect 24 ml of blood for research when the subject has blood drawn for routine labs (if applicable) . Women of child-bearing potential will undergo a urine pregnancy test as per indicated clinical care. We will enter the results of routine labs as well as results from the B cell analysis in our study database.

**Visits 19 - 20 (Weeks 100 - 106):** The subject will have a routine clinical evaluation and a BVAS assessment. We will collect information on adverse events, concomitant medications, and medication compliance. Women of child-bearing potential will undergo a urine pregnancy test as per indicated clinical care. We will enter the results of routine labs in our study database.

At week 106, subjects will have 24 ml of blood drawn for research purposes, including analysis of B cell counts.

At week 106, all subjects will undergo a CDA assessment by the nephrologist.

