## Grading the Severity of Adverse Events (Common Terminology Criteria for Adverse Events v.4.0[CTCAE])

### Grades

Grade refers to the severity of the AE. The CTCAE displays Grades 1 through 5 with unique clinical descriptions of severity for each AE based on this general guideline:

- **Grade 1:** Mild; asymptomatic or mild symptoms; clinical or diagnostic observations only; intervention not indicated.
- **Grade 2:** Moderate; minimal, local or noninvasive intervention indicated; limiting age-appropriate instrumental activities of daily living\*. An infection requiring oral antibiotics and resulting in interruption of school or work ≤1 day, is considered a Grade 2 infection.
- **Grade 3:** Severe or medically significant but not immediately life-threatening; hospitalization or prolongation of hospitalization indicated; disabling; limiting self-care activities of daily living\*\*. An infection requiring hospitalization or IV antibiotics or resulting in interruption of school or work > 1 day will be considered a Grade 3 infection
- **Grade 4:** Life-threatening consequences; urgent intervention indicated.
- **Grade 5:** Death related to AE.

\*Instrumental activities of daily living refer to preparing meals, shopping for groceries or clothes, using the telephone, managing money, etc.

\*\*Self-care activities of daily living refer to bathing, dressing and undressing, feeding self, using the toilet, taking medications, and not bedridden.

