### **Adverse Event Reporting Period**

The study period during which adverse events will be reported will be defined as the period from the initiation of any study procedures to the end of the study treatment follow-up. For this study, the study treatment follow-up is defined as 30 days following the last administration of study treatment.

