## **8.2 Recording of Adverse Events**

At each contact with the subject, the investigator will seek information on adverse events by specific questioning and, as appropriate, by examination. Information on all adverse events will be recorded immediately in the source document, and also in the appropriate adverse event module of the case report form (CRF). All clearly related signs, symptoms, and abnormal diagnostic procedure results will be recorded in the source document, though grouped under one diagnosis.

All adverse events occurring during the study period will be recorded. The clinical course of each event will be followed until resolution, stabilization, or until it has been determined that the study treatment or participation is not the cause. Serious adverse events that are still ongoing at the end of the study period will be followed up to determine the final outcome. Any serious adverse event that occurs after the study period and is considered to be possibly related to the study treatment or study participation will be recorded and reported immediately.

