Given the small number of patients in each treatment group in our proposed proof of concept trial (~15 patient per group), it is difficult to decide a priori of a number of relapses in the No-maintenance therapy group that would prompt termination of the trial. We propose prompt consideration of early termination of the trial if the following criteria are met at any point over the course of the trial (provided a sufficient number of patients are accrued and randomized):

- 1)  $\geq 50\%$  major relapse rate in the NO-maintenance therapy group, AND
- 2)  $\geq 40\%$  major severe relapse rate over the maintenance therapy (control) group. Major relapse is defined as involving a major organ or life threatening (e.g. alveolar hemorrhage, glomerulonephritis, mononeuritis with new motor deficits).

The DSMB will be contacted for a review of the study outcomes whenever 2 new relapses have occurred in the NO-maintenance therapy (surveillance) group.

The " $\geq 40\%$  major severe relapse rate over the Maintenance Therapy Group" criterion stems from the small number of patients anticipated in each of the randomized groups ( about 15 per group) and for the recognized potential relapse rate in the control (maintenance immunotherapy) group (in the MAINRITSAN trial, the major relapse rates were 5% and 29% over 28 months for the rituximab and azathioprine groups respectively) (Guillevin L et al *N Engl J Med* 2014;371:1771-80.).

During the conduct of the trial, and before all the patients are accrued, a threshold of 50% relapse rate may be attained with a very small number of events (1-2). The additional  $\geq 40\%$  over the Maintenance Therapy criterion is meant to verify that the study is not terminated prematurely by a chance event.

Conversely, we propose the following criterion to prompt consideration of early termination of the trial for toxicity if there is a  $\geq 40\%$  increase in Grade 3 severe serious adverse event rate in the maintenance therapy (control) group compared to the NO-maintenance therapy group.

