#### Treatment Stopping Rules:

We do not have criteria for withdrawing individual subjects from the study.

If a subject in either treatment group (maintenance therapy or no maintenance therapy group) relapses, s/he will receive treatment at the discretion of the nephrologist managing his/her care. That will end the interventional phase of the subject's participation. However, we will continue to follow the subject (collect information and blood) for the full 24 months of post randomization follow up.

If a subject in the maintenance therapy group experiences a non-infectious adverse event attributable to the maintenance medication (e.g. allergic reaction) s/he is receiving (rituximab, azathioprine, MMF), this medication will be discontinued and the patient will be switched to another immunosuppressive medication per the patient's treating nephrologist.

Infectious adverse events are common in all forms of immunosuppressive therapy. Severe (Grade 3) infectious adverse events will result in temporary interruption of azathioprine or MMF therapy, or postponement of rituximab therapy, until the infection is fully treated. Grade 4 infectious adverse events will lead to the permanent discontinuation of maintenance immunosuppressive therapy. Grade 3 infectious adverse events may also lead to permanent discontinuation of maintenance immunosuppressive therapy based on the judgement of the treating physician.

If a subject in the maintenance therapy group wishes or needs to discontinue therapy, therapy will be stopped. That will end the interventional phase of the subject's participation. However, we will continue to follow the subject (collect information and blood) for the full 24 months of post randomization follow up.

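### The toxicity criterion for early termination names Grade 3 only, and the adverse-event reporting period does not give the two arms one common window

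*Combined protocol and SAP*

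**What the plan says.** **The criterion.** Section 8.4 sets a numerical toxicity criterion, on which early termination would be considered: a 40% or greater "increase in Grade 3 severe serious adverse event rate in the maintenance therapy (control) group" compared with the no-maintenance group. It does not say Grade 3 or higher, and it does not say whether 40% is an absolute or a relative difference.

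**The grades.** Section 8.1 (Grading the Severity of Adverse Events) gives Grade 4 its own definition, "Life-threatening consequences; urgent intervention indicated", and reserves Grade 5 for death. Section 8.4 (Treatment Stopping Rules) describes one consequence for Grade 3 infections and another for the next grade: "Grade 4 infectious adverse events will lead to the permanent discontinuation of maintenance immunosuppressive therapy".

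**The window.** Section 8.1 (Adverse Event Reporting Period) runs from the first study procedure to the end of treatment follow-up, where "the study treatment follow-up is defined as 30 days following the last administration of study treatment".

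**Collection.** Section 8.2 says "At each contact with the subject, the investigator will seek information on adverse events by specific questioning". The schedules in Section 6.3 mark adverse events at every clinic visit after randomisation in both groups, to week 106 in WATCH. For patients who relapse or stop therapy, Section 8.4 says "we will continue to follow the subject (collect information and blood) for the full 24 months of post randomization follow up".

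**The concern.** The criterion is meant to detect excess toxicity from maintenance immunosuppression. If it is applied as worded, a patient whose only event was life-threatening or fatal does not count, while one with a Grade 3 event does. The sections that define and use the grades do not support reading Grade 3 as a label for everything severe.

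The window is a separate problem. A between-arm comparison needs the same period of observation in each arm. An end date tied to the last administration of study treatment has no meaning in WATCH, and in the rituximab group it is shortest for patients who stopped early, some of them because of toxicity.

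The Section 8.4 criteria are the plan's only numerical grounds for considering termination. The proof-of-concept text in Section 1.1 adds that meeting the stopping rules would make the team cautious about a further trial with this marker. What these criteria count therefore bears on more than the DSMB's agenda.

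**Working it through.** **Inputs.** About 31 of 40 patients randomised (Section 7.1) and about 15 per group (Section 8.4); infusions at weeks 0, 22, 46, 70 and 94, each ±1 week (notes to the treatment-group schedule, Section 6.3); last scheduled assessment at week 106; window end = last treatment + 30 days (Section 8.1); threshold 40% (Section 8.4). The plan's own figures reproduce: 31/40 = 77.5%, given as 78%, and 31/2 = 15.5 per group.

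**Step 1, grade, by counting.** Suppose 6/15 maintenance patients have Grade 4-5 events only and 0/15 in WATCH have any. Counting Grade 3 or higher: 6/15 − 0/15 = 40 points, which meets the threshold on an absolute reading. Counting Grade 3 literally: 0/15 − 0/15 = 0.

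**Step 2, grade, by probability.** Assumptions, none from the documents: true proportions with a Grade 3-5 serious event of 50% (maintenance) and 10% (WATCH); a share s of affected patients, equal in both arms, with Grade 4-5 events only; 15 per arm; one look; absolute reading; rate taken as the proportion of patients. The literal criterion sees 0.50(1 − s) and 0.10(1 − s). The chance of meeting it is the sum of P(M = m)·P(W = w) over all m − w ≥ 6, with M and W binomial:

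| s | rates counted | chance of meeting criterion |
|---|---|---|
| 0 | 50% vs 10% | 59% |
| 0.1 | 45% vs 9% | 49% |
| 0.2 | 40% vs 8% | 37% |
| 0.3 | 35% vs 7% | 27% |

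**Step 3, window.** Closing week = infusion week + 30/7:

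| last infusion | window closes | weeks left to week 106 | share of 106 weeks |
|---|---|---|---|
| week 94 | 98.3 | 7.7 | 7% |
| week 70 (then stopped) | 74.3 | 31.7 | 30% |
| week 46 (then stopped) | 50.3 | 55.7 | 53% |
| WATCH (none given) | undefined | – | – |

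With the ±1 week visit window, the first row closes between weeks 97.3 and 99.3. Patients who take daily azathioprine or mycophenolate to the end are not affected.

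The two faults can fall on the same event. Take an infusion at week 70 and a Grade 4 infection at week 80. Maintenance is then permanently discontinued, so week 70 becomes the last administration and the reporting period closed at week 74.3. The event that caused the discontinuation lies outside the period, and its grade also keeps it out of the criterion.

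**Step 4, what 40% means.** With equal true toxicity rates in both arms, 15 per arm and one look, the chance of meeting the criterion (relative reading: ratio of at least 1.4, with 0 against 1 or more counted as an increase) is:

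| true rate, both arms | absolute | relative |
|---|---|---|
| 10% | 0.06% | 37% |
| 20% | 0.6% | 34% |
| 30% | 1.3% | 29% |
| 40% | 1.9% | 25% |

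**Step 5, effect of a common window.** Counting to 24 months includes events after a WATCH relapse, when patients are re-treated (Sections 4.4 and 8.4). If that raised the WATCH rate in step 2 from 10% to 20% or 30% (assumed) with maintenance at 50%, the chance of meeting the criterion, all grades counted, would fall from 59% to 35% or 17%. A common window alone could therefore mask maintenance toxicity.

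**The case against.** **Grade 3 is probably shorthand.** The definition of serious in Section 8.1 expressly includes fatal and life-threatening events, Section 8.5.1 asks the DSMB to review frequency and severity by arm, and Appendix A has the investigator supply all adverse-event reports. This stands as a limit on the consequences: a reader might infer that the worst events would go unseen, and the documents do not support that. It does not repair the criterion, which still names one grade of several.

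**The window conflict may lose no data.** Events are sought at each contact and marked at every visit. A reader might infer from Section 8.2, which requires recording and reporting of "Any serious adverse event that occurs after the study period and is considered to be possibly related to the study treatment or study participation", that nothing else is recorded after the period ends. The section does not say so. Nor does any section tie the Section 8.4 criterion to the Section 8.1 reporting period. Both points stand, so what remains is an unresolved conflict over which events are counted. For patients treated to week 94 the gap also comes at the end of follow-up, where an early-termination rule has least to do.

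**The relapse rule might be thought equally faulty.** Section 8.4 relies on its second relapse criterion (40% over control) to prevent a chance stop. On an absolute reading, with WATCH exactly at 50%, that criterion is met whenever control relapse is 10% or less, so a reader might infer that the guard fails. It guards mainly when control relapse is high, which is where chance crossings are common. By exact binomial calculation with equal rates in both arms, it blocks 43% to 86% of crossings at 29% relapse (2 to 15 per arm). At 5% relapse and 4 per arm it blocks 18%, but only 1.4% of trials cross at all. One relapse among two WATCH patients reaches neither DSMB review point (2 new WATCH relapses, or 8 patients randomised).

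**Conclusion.** The concern holds for the toxicity criterion. As worded it leaves out Grades 4 and 5, against the protocol's own grading and its own separate use of Grade 4. The 40-point example is arithmetic; the fall from 59% to between 49% and 27% rests on assumed rates and shares and shows direction and rough size only.

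The window concern holds in a smaller form. The reporting period has no end in WATCH, closes 7.7 weeks early after a week-94 infusion and 31.7 or 55.7 weeks early if rituximab stops after week 70 or 46. It conflicts with collection to 24 months, so the content of the between-arm comparison is not fixed. The effect on the criterion itself cannot be computed from the documents.

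The documents do not support going further, to a claim that safety oversight fails or that the relapse rule needs a numerical minimum in place of its unquantified proviso on accrual. The criteria prompt consideration only, beside general DSMB review. A minimum would also be a trade-off. In a simulation requiring 8 randomised and at least 3 WATCH major relapses, with 24-month major relapse risks of 50% against 5%, the chance of meeting the rule during accrual fell from 14% to 10%. That simulation assumed 31 patients randomised evenly over 24 months, constant relapse hazards, the crude share of randomised patients as the rate, and an absolute 40%.

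**What to change.** Keep the sponsor's 50% and 40% thresholds.

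1. Reconcile the toxicity criterion in Section 8.4 with the grade definitions in Section 8.1 and the infection rules in Section 8.4, so that the criterion counts Grade 3 or higher.
2. Reconcile the reporting period in Section 8.1 with Sections 6.3, 8.2 and 8.4. For this comparison, count serious events in both arms from randomisation to the 24-month visit, whatever their judged relation to treatment.
3. Show the same comparison with events censored at first relapse, for the reason in step 5. Give follow-up time by arm beside it, since censoring shortens follow-up most in the arm with more relapses.
4. State how the Section 8.1 exclusion of hospitalisation for the target disease applies to this count.

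For clarification with the DSMB, which under Appendix A sets monitoring and reporting requirements with the investigator and biostatistician: state whether each 40% is absolute or relative, and note that the second relapse criterion protects mainly when control relapse is high. A numerical minimum is optional.

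**Cost.** Wording in Sections 8.1, 8.2 and 8.4 and one short table with two versions of the count. No new visits are needed, because adverse events are already collected at all scheduled visits after randomisation. The price of the common window is the possible masking described above, which the censored version is there to show.

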#### Treatment Stopping Rules:

We do not have criteria for withdrawing individual subjects from the study.

If a subject in either treatment group (maintenance therapy or no maintenance therapy group) relapses, s/he will receive treatment at the discretion of the nephrologist managing his/her care. That will end the interventional phase of the subject's participation. However, we will continue to follow the subject (collect information and blood) for the full 24 months of post randomization follow up.

If a subject in the maintenance therapy group experiences a non-infectious adverse event attributable to the maintenance medication (e.g. allergic reaction) s/he is receiving (rituximab, azathioprine, MMF), this medication will be discontinued and the patient will be switched to another immunosuppressive medication per the patient's treating nephrologist.

Infectious adverse events are common in all forms of immunosuppressive therapy. Severe (Grade 3) infectious adverse events will result in temporary interruption of azathioprine or MMF therapy, or postponement of rituximab therapy, until the infection is fully treated. Grade 4 infectious adverse events will lead to the permanent discontinuation of maintenance immunosuppressive therapy. Grade 3 infectious adverse events may also lead to permanent discontinuation of maintenance immunosuppressive therapy based on the judgement of the treating physician.

If a subject in the maintenance therapy group wishes or needs to discontinue therapy, therapy will be stopped. That will end the interventional phase of the subject's participation. However, we will continue to follow the subject (collect information and blood) for the full 24 months of post randomization follow up.

## **8.5 Safety Monitoring**

### **8.5.1 Internal Data and Safety Monitoring Board or DSMB**

We will use the UNC North Carolina Translational & Clinical Sciences Institute (NC TraCS) DSMB.

The Charter of the NC TraCS DSMB is included in Appendix A, detailing the members, protocol review and monitoring process. The protocol is submitted for review by the DSMB. Changes (if any) to the DSMB monitoring plan will be developed in accordance with DSMB recommendations. We request that DSMB review of the study be started when 8 patients have been randomized to NO maintenance vs maintenance immunosuppression, and every 6 months thereafter. We also request that the DSMB review the frequency and severity of adverse events and relapses in the NO maintenance compared to the maintenance immunosuppression groups.

The NC TraCS DSMB monitors studies for safety and/or efficacy. Source document data monitoring for accuracy and completeness will be done by a UNC Research Coordinator NOT involved in this study, who will review CRFs and source documentation on a regular basis to determine proper adherence to the protocol with collection of all relevant documentation to support the study.

## **9 Data Handling and Record Keeping**

### **9.1 Confidentiality**

Information about study subjects will be kept confidential and managed according to the requirements of the Health Insurance Portability and Accountability Act of 1996 (HIPAA).

Patients will be assigned unique study IDs which will be used on hard copy documents for identification purposes in lieu of personal identifiers. Personal identifiers will be redacted on paper documents which print with identifiers

(e.g. medical records). Study binders will be stored in a locked cabinet in UNC Kidney Center office space which is locked during off hours. These documents will be kept in secure long-term storage for the period of time required by institutional and FDA regulations and will then be shredded and disposed of securely.

We will create a screening log in Excel. This log will be password protected and maintained on a secure UNC Kidney Center server. Only authorized study personnel will have access to this file. We will collect only the minimum amount of information necessary for screening purposes. This will include name and medical record number so that we can keep track of which patients have been screened and evaluate patient eligibility for the study on an ongoing basis if needed (e.g. track treatment and disease status). This log will be deleted once enrollment is closed.

We will create a REDCap database which will store demographic, clinical, and research data. This database will be password protected and will reside on a secure UNC Kidney Center server. Only authorized study personnel will have access to this file. We will collect data on demographics, routine labs, BVAS and CDA scores, B cell counts, AEs, concomitant medications, medication compliance, and quality of life. This file will be deleted once data analysis has been completed.

Biological samples will be labeled with the subject's study ID and a unique bar code. These samples will be tracked in the IRB-approved GDCN database. Samples will be destroyed once the study is completed, including data analysis.

## **9.2 Source Documents**

Source data will be drawn from the following source documents: records contained in the UNC electronic record, including clinic notes, inpatient notes, laboratory results, pathology reports, operative notes, radiology reports, procedure notes and documents from outside sources which have been scanned into the electronic record. Source documents will also include assessment forms completed by study physicians (CDA and BVAS), case report forms, and questionnaires completed by the subjects.

